The reasons why women do not attend for screening are well documented [3-7] with a lack of evidence relating to effective solutions to help women overcome their perceived barriers to screening. In summary these include: a fear of cervical smears and speculum examination, a lack of understanding of the purpose of screening, underestimating the risk of developing cervical cancer, problems accessing convenient screening appointments, not having the time to attend for screening and not being able to afford the costs associated with attending a screening appointment. There is the additional problem of younger women being a transient population who are out of contact with health

services and consequently at risk of becoming lost to the system and not receiving an invitation to screening. The combination of these barriers and the lack of evidence regarding successful interventions indicate that there is not one single solution to the problem of the declining number of young women attending for screening. With this in mind, the interventions selected for evaluation have been designed to appeal to a range of young women based on the principle that ‘one size does not fit all’.

1.2 Existing research in relation to proposed interventions

Cervicovaginal self testing for high risk HPV has been shown to be as sensitive as ‘physician obtained specimens’ in terms of detection of cervical intraepithelial neoplasia.[8] In a publication earlier this year from the Netherlands, self testing for high risk HPV was taken up by 25% of women who had failed to attend for screening. 10% were HPV+ve, and 90% followed up with their general practitioner regarding cytology. Of these women CIN2 or worse was found in 14% (1.5% of the entire self test group).[9] Internet booking has not, to our knowledge, been used for booking cervical screening appointments. Timed appointments for non-responders have previously been shown to be effective in an osteoporosis screening programme where a reminder letter was sent to women asking them to confirm their attendance at a specified appointment or risk having the appointment cancelled by the care provider.[10] Nurses are widely used to offer support and guidance to patients on a daily basis, we believe that having a nurse who is easily accessible to women who wish to discuss their concerns about cervical screening will help to allay their fears and ‘navigate’ them to overcome barriers to attending for screening appointments.

1.3 Addressing health inequality

We recognise that cervical screening coverage is much poorer amongst socially deprived and ethnic minority groups. Greater Manchester therefore represents an excellent setting with diversity across social and ethnic groups all of whom would have access to our community based study which will include the entire PCT catchment. Cervical screening is of course offered to all and our project is therefore aimed equally at women in the hope that our strategies will be of particular relevance to those women most in need of improvement over current arrangements.

1.4 Population to be studied

The population to be studied in this trial is young women aged 19 and a half or 24 and a half in Greater Manchester and Aberdeenshire, who will be receiving their first invitation for cervical screening. These women will be drawn from all general practices in the area and will be socio-demographically representative of women receiving their first invitation for cervical screening across the UK.

2. Trial Objectives and Purpose

2.1 Purpose of trial

The purpose of this trial is to determine whether a range of complex interventions designed to improve young women's receptivity to, and uptake of, cervical screening are successful when embedded within routine cervical screening programme practice

2.2 Objectives

Phase 1

[figure not shown]
1. To determine the value of a pre-first invitation leaflet which has been designed to increase receptivity of young women to cervical screening. The development of this leaflet has been completed prior to this study, and is based on focus group work with young women which targeted issues which influence them (North West 2, Reference 10/H1005/47).
2. To determine the feasibility, acceptability, effectiveness and cost effectiveness of offering internet booking as an alternative to phoning the GP as a means of making an appointment at first invitation.

Phase 2

3. To determine amongst those women who fail to attend after a first reminder, the feasibility, acceptability, effectiveness and cost-effectiveness of several novel strategies: a) self sampling for HPV status as a determinant of the need for cervical cytology, b) a specialist nurse 'navigator' to help a woman overcome her barriers to screening, c) timed appointments for cervical screening to encourage women to attend d) a choice of HPV self sampling or the nurse navigator.
4. To determine amongst women in Scotland, who have recently been offered HPV vaccination as part of the national catch-up campaign:
 - a) the first invitation uptake following the pre-invitation leaflet (phase 1)
 - b) the uptake amongst those who have failed to attend following a first reminder letter, as a result of the novel strategies mentioned in objective no. 3.
5. To estimate the costs and cost-effectiveness of each of the strategies for improving cervical screening uptake.
6. As well as estimating the effects of individual interventions we will estimate the effectiveness and cost effectiveness of packages of interventions.

3. Trial design

3.1 Flow diagram

3.2 Research methods

The research methods have all been validated and are used routinely. The feasibility of some interventions will be evaluated in pilot studies (see below). Our research proposals address equity of access, through the project including a PCT with one of the worst rates of cervical screening uptake in England despite cervical screening being universally available. Our study will involve women in general practices across the entire Manchester, Salford and Trafford PCT and Aberdeenshire catchment. This includes practices with a range of social deprivation and screening coverage amongst the study age group. The screening invitation is automatically sent to every woman registered with a general practice so screening is available to all.

3.3 Planned Interventions

3.3.1 Pre-call cervical screening information leaflet (pre-leaflet)

Women in England aged 24 and a half years will be sent a bespoke information leaflet around six weeks prior to their first invitation. The content of this leaflet has been informed by focus groups and consultation exercises with women aged around 24 in Manchester and 19 in Aberdeen. The rationale will be to convert them from ‘pre-contemplators’ to ‘contemplators’ (based on the Transtheoretical model) by the time the standard NHSCSP invitation is received. This will deal with key themes and issues that emerged from the focus group and consultation work which has already been completed. Leaflets produced for use with the Aberdeen cohort will be sent to young women aged 19 years who are deciding whether to accept their invitation for cervical screening. They will have recently been offered HPV vaccination and the leaflet should be equally applicable to vaccinated women in England when they begin to receive their invitations 5 years from now.

In Manchester and Aberdeen the pre-leaflet will be sent to eligible women (i.e. those aged 24 and a half or 19 and a half) in randomised practices. This will be facilitated by the local screening agencies who maintain the population based register for the cervical screening programme and routinely have access to women’s details.

The outcome of this intervention will be the proportions of women screened in the intervention and control practices measured primarily at 2-3 months, prior to the first reminder and secondarily at 12 month. These data will be provided by the local screening agencies who routinely monitor the screening uptake in the practices within the boundaries of the Primary Care Trusts for which they are responsible. The screening agency will create an anonymised record for each woman involved in the trial using a unique identifier.

3.3.2 Internet booking

Women in surgeries randomised to receive the internet booking intervention will receive a letter providing them with information on how to make an internet booking and a list of participating clinics. This information will be sent with their first invitation letter and with the first reminder letter from the screening agency, which is sent to women without a test recorded three months after their test due date. An online appointment scheduling system will be used (<http://www.supersaas.com/>), to which women will be directed from a webpage held on a University of Manchester server. A separate appointment schedule will be created for each clinic in the Palatine Contraception and Sexual Health Service, which will only show available appointments to users who are not logged in to the system. Women accessing the service will be asked to input only their name and a contact number, and will not be able to see appointments that have been booked by other users. An administrator account will be held for the system by the research team, who will forward on details of booked appointment to an administrator at the Palatine clinics using the NHS.net email system. Family Planning staff will be asked to indicate whether a woman who had booked online had attended and consented to screening. Women will be informed of who will be able to access the data held on the booking system when they access the system to book an appointment.

The number of women using the system and attending for cytology will be recorded. Local screening agencies will be asked to supply screening uptake data for all women in the trial on an individual level in both the control and intervention practices in order to ascertain the proportion of cytology that was obtained as a result of internet booking. The outcome of this intervention will be measured at 5 months post call, prior to the second reminder.

3.3.3 Human Papillomavirus (HPV) self sampling

Women in surgeries randomised to receive the HPV self sampling intervention will receive a letter describing the study in a second reminder letter from the screening agency, which will be sent to women without a test recorded six months after their test due date. The letter will explain the purpose of HPV self sampling, how the test is taken and the implications of the test results. Women will be given details of how to contact the trial office and request a self sampling kit by phone, text message or email.

A self sampling kit will be sent to women which comprises the following:

1. A self sampling kit.(either Delphi lavage or The Rovers® Evalyn-Brush)
2. Return sample packaging compliant with transport regulation UN3373 for Category B Biological Substances.

3. An information sheet explaining the purposes of the test, how the results will be conveyed to the woman and her General Practitioner, the implications of the results and instructions on both taking the vaginal sample and returning it to the Virology laboratory.
4. A consent form for processing the sample, reporting the results to the woman (giving her the option of not having correspondence to her home address) her GP and local screening agency and also seeking permission for the research team to check the Exeter screening database for subsequent cytology samples in the event of a positive result.

Women will return the sample to the Manchester Virology Laboratory using a postage paid UN3373 compliant overpack envelope. The sample will be processed and the result sent to the trial staff who will notify the woman, her GP and the screening agency of the result (unless the woman explicitly expresses a wish for her GP not to be informed). Women who test HPV positive will be advised to attend for cytology screening and will be sent a results letter advising them of how to arrange a screening test with either their GP or local family planning service. GPs will also be advised of any management recommendations made to the woman. Any woman receiving a positive HPV result will also be given the contact details of the study nurse should they wish to discuss their result. Recording of HPV results on the NIHS Exeter database has not been possible to operationalise in the study time frame. Therefore, recall of HPV positive women for cytology will be the responsibility of the research team. In the event that women testing positive have not subsequently attended for cytology 12 months after the self-sampling intervention the research team will send a reminder to the woman. Women testing HPV negative will be reassured and will revert to routine recall.

The number of women both requesting and returning the HPV self sampling kits will be monitored directly by the trial office. Specific consent will be sought from the women to check for the presence of a cytology sample on the national screening database in the event of a HPV positive result, allowing the researchers to monitor compliance with management recommendations. Local screening agencies will be asked to supply anonymised screening uptake data for all women in the trial in both the control and intervention practices at an individual level in order to ascertain the proportion of cytology that was obtained as a result of women testing HPV positive by self sampling. The outcome of this intervention will be measured primarily at 12 months and secondarily at 30 months post call.

3.3.4 Nurse navigator (NN)

Women in surgeries randomised to receive the NN intervention will receive a letter describing the study together with a second reminder letter from the screening agency, which will be sent to women without a test recorded six months after their test due date. The letter will provide contact details and explain how the NN may be able to offer help and advice, and to allay any anxieties they might have regarding attending for a cervical screening test. Women will be encouraged to contact the NN via phone to speak to her directly during daytime hours, or to contact the trial office via phone, email or text messaging to request that the nurse navigator calls them at a convenient time. The NN will discuss the woman's perceived barrier(s) to accepting her invitation for cervical screening and assist the woman in booking an appointment if necessary. If the nurse deems internet booking or HPV self sampling to be appropriate to the woman's needs she would facilitate access to these interventions. Written consent for follow up will be sought by the nurse at the time of the woman making contact with her. Consent forms and an information sheet will be sent to the woman, with her permission, so she is able to provide written consent to her details being stored in the trial's database and used to check for the presence of a cytology sample on the national screening database, allowing the researchers to monitor compliance with screening after contact with the nurse navigator. Women would also be asked if they would like to receive a follow up call from the nurse navigator to discuss whether they had arranged/attended for screening.

The number of women contacting the NN will be monitored directly by the trial office. Local screening agencies will be asked to supply anonymised screening uptake data for all women in the trial on an individual level in both the control and intervention practices in order to ascertain the proportion of cytology that was obtained as a result of women contacting the nurse navigator. The outcome of this intervention will be measured primarily at 12 months and secondarily at 30 months post call.

Nurse Navigator (NN) Training

The following NN training programme is envisaged:

- 1) cervical cancer and HPV knowledge
- 2) logistics of HPV self sampling and cytology test procedure
- 3) implications of results of HPV, advice if –ve/ +ve
- 4) principles of motivational interviewing
- 5) structured interviewing skills
- 6) assessment of women's readiness for screening
- 7) approaches for women who are ambivalent towards attending for cervical screening (contemplation), or are ready to act (action)

Description of the role of the NN

The optimal means of contacting the nurse navigator, hours of access, interaction with practice nurses, are all issues which will be addressed during the piloting of the nurse navigator role along with other interventions during the first years of the project.

NN's would conduct a semi structured interview over the phone to identify barriers to screening and talk through suitable options for overcoming these:

- supportive contact with the woman by telephone
- improve women's understanding of the importance of cervical cancer screening
- offer HPV self testing if appropriate. The NN could also offer to review the HPV self testing instructions with the woman again over the phone once the woman has received the pack
- encourage the woman to become active (attend screening). For women who following discussion of barriers intend to attend screening, the NN could discuss the test procedure and provide information for the woman to arrange a screening appointment (internet appointment booking system).
- follow-up on test scheduling (reminder call: NN call the woman one day prior to their screening appointment.
- follow-up on results
- to provide reassurance
- address language needs e.g. link worker at GP

NN keep records of interactions with patients, including frequently asked questions.

To standardise the way that the NN's respond to women, a manual will be written containing the Standard Operating Procedure (including frequently asked questions) and patient educational materials.

3.3.5 Timed appointments

GPs will be asked to send women an invite letter detailing a time and date for them to attend for a cytology appointment. In this invite letter women will be given the option to rearrange for a more convenient time if needed. Local screening agencies will be asked to supply anonymised screening uptake data for all women in the trial on an individual level in both the control and intervention practices in order to ascertain the proportion of cytology that was obtained as a result of timed appointments. The outcome of this intervention will be measured primarily at 12 months and secondarily at 30 months post call.

3.4 Piloting of Planned Interventions

Each of the proposed interventions in phase 2 would be piloted in Manchester during the timeframe of phase 1. Women aged 25.5 to 27.5 years i.e. those women who have failed to attend for their first cervical screening despite reminders, will be targeted. We will use the methods proposed in phase 2 to contact women and to offer the interventions in the ways described. The purpose of these pilots is to evaluate the feasibility of the intervention e.g. arranging pre-booked appointments, the practicalities e.g. the arrangements for self testing, the accessibility of our proposals to these women, and most importantly the uptake of screening as a result. We aim to target 720 women and offer 120 each of the intervention options; i.e. i) nurse navigator, ii) offer of ordering a self-sampling, iii) unsolicited mailing of two different self sampling kits, iv) timed appointments, a choice of i) and ii), with 120 being offered no intervention. Interventions will be taken forward to phase 2 if the null hypothesis of a two-sample test of proportions comparing the uptake rate in the pilot interventions and the control is rejected at a one-tailed 25% significance level. In addition, the piloting phase will include a discrete choice experiment (DCE) on non-responding women identified by the screening agency who are not directly involved in the pilot study (see section 6). The piloting would involve 2-3 months of offering the interventions, 3-4 months of follow up including qualitative interviews and 2 months for analysis.

3.5 Proposed outcome measures

The primary outcome measure for all interventions is attendance for cervical screening which will be obtained from the Exeter Information System. This will be measured at 3 months post-call (prior to the first reminder letter), 12 months post-call and 30 months post-call (prior to the next recall). The primary endpoint for the pre-leaflet and online booking will be uptake at 3 months post-call. The primary outcome for the self-sample, the nurse navigator and timed appointment intervention will be uptake at 12 months post-call.

The main outcomes of the study are estimates of:

1. The uptake of cervical screening:
 - a) In response to the pre-leaflet (phase 1).
 - b) In response to the offer of each of the interventions (phase 2).
2. The uptake of internet booking (phase 1).
3. The differences between outcomes in Aberdeen between vaccinated and unvaccinated women.
4. The differences between Aberdeen and Manchester.
5. Cost-effectiveness of the interventions, individually and as packages of interventions.

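### Phase 2 primary outcome counts only attendance recorded on Exeter, so a completed HPV-negative self-test is scored as non-attendance

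*Protocol*

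**What the plan says.** Protocol section 3.5 fixes both the outcome and its source: "The primary outcome measure for all interventions is attendance for cervical screening which will be obtained from the Exeter Information System". For the arms at issue it adds the time point: "The primary outcome for the self-sample, the nurse navigator and timed appointment intervention will be uptake at 12 months post-call". Section 5.2 again names Exeter as the source of the attendance data.

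Section 3.3.3 describes what happens to a self-test:

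- On recording: "Recording of HPV results on the NIHS Exeter database has not been possible to operationalise in the study time frame".
- On a negative result: "Women testing HPV negative will be reassured and will revert to routine recall".
- The agency data for this intervention are meant to "ascertain the proportion of cytology that was obtained as a result of women testing HPV positive by self sampling".
- Kit requests and returns are tracked by the trial office. Nothing says that they enter the primary outcome.

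Section 2.2, objective 3a, gives the purpose as "self sampling for HPV status as a determinant of the need for cervical cytology". Section 5.1.2 nevertheless powers the self-test arms on the same attendance difference, 10% against 20%, as the other arms.

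**The concern.** Self-sampling is offered as a triage test, and a negative result removes the need for cytology. Cytology attendance is the event that the primary outcome counts, so the intervention works largely by making that event unnecessary. Read together, sections 3.5 and 3.3.3 let a self-tester register only if she is HPV positive and then attends, or if she attends regardless of her result.

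The self-test-sent and self-test-offered arms (31 and 34 practices in Figure 2) are fully exposed. The choice arm is partly exposed, because attendances prompted by the nurse still count. The nurse navigator arm is partly exposed because section 3.3.4 lets the nurse arrange a kit.

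The phase 2 primary comparison could show little or no effect for a strategy that reached many women. The cost per percentage point of attendance in section 6 would carry the cost of the kits while leaving out most of the women who used them. Objective 3a, on effectiveness and cost-effectiveness of self-sampling, would not be answered.

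**Working it through.** **Inputs from the protocol**

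- Section 1.2, cited Dutch cohort: 25% of non-attenders took up the self-test, and "10% were HPV+ve, and 90% followed up with their general practitioner regarding cytology".
- Section 5.1.2: 10% against 20%, 20 women per practice, 30 practices per intervention arm, 100 control practices, ICC up to 0.07, Bonferroni correction for 5 comparisons.
- Section 5.1.1: the phase 1 ICC is 0.026.
- Assumed, since it is not stated: overall two-sided 0.05, so alpha = 0.05/5 = 0.01 and z = 2.576.

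**Step 1. Reproduce the plan's power**

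Design effect = 1 + ((1 + CV²) × 20 − 1) × ICC, where CV is the coefficient of variation of cluster size. With equal clusters and ICC 0.07 it is 1 + 19 × 0.07 = 2.33. Effective sizes are 2000/2.33 = 858 control and 600/2.33 = 258 intervention women.

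Power = Φ[(d − 2.576 × SE0)/SE1], with SE0 pooled and SE1 unpooled. For 10% against 20%, d = 0.10, SE0 = 0.0233 and SE1 = 0.0270, so power is 93%. It is 89% at CV 0.5 and 82% at CV 0.8. The stated figure of more than 80% is reproduced.

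**Step 2. What can register as attendance**

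Countable gain = self-test uptake × HPV-positive share × share going on to cytology = 0.25 × 0.10 × 0.90 = 0.0225, or 2.25 points. That is 9% of the 25 points of self-testing. The HPV-negative part, 0.25 × 0.90 = 22.5 points, is scored as non-attendance.

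**Step 3. Power for 10% against 12.25%**

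- ICC 0.07: SE0 = 0.0218 and SE1 = 0.0229. Power is 7.0% with the formula above and 5.6% with the unpooled variance throughout. The Figure 2 numbers (97 and 31 practices) give 7.1% and 5.7%.
- ICC 0.026: the design effect is 1.494 and power is 11%.

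**Step 4. Higher HPV positivity**

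The documents give only 10%, so the other rates are assumptions (25% uptake, 90% follow-up, ICC 0.07, alpha 0.01, equal clusters):

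| HPV positive | Countable gain | Power |
|---|---|---|
| 10% | 2.25 points | 7% |
| 20% | 4.5 points | 30% |
| 30% | 6.75 points | 64% |
| 40% | 9.0 points | 87% |

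**Step 5. If self-testers replace attenders**

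Suppose self-testers would otherwise have attended at the 10% control rate, and those testing negative now forgo cytology. Exeter would show 0.75 × 10% + 2.25% = 9.75%, against 10% in control. The recorded gain is about nil.

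**Step 6. If completed self-tests counted**

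Counting negatives, and positives with cytology, gives 22.5 + 2.25 = 24.75 points and power above 99% at ICC 0.07. Counting every valid result adds the positives without cytology, 0.25 × 0.10 × 0.10 = 0.25 points.

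**Timing**

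The 30-month endpoint does not help, because section 3.5 places it before the next recall. Kits are offered at about six months, and HPV-positive women without cytology are reminded 12 months after self-sampling. That reminder falls after the 12-month primary time point.

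**The case against.** - **No sentence says that a negative self-test is scored as unscreened.** This is true; it follows from two sections read together. Section 3.5 also speaks of uptake in response to each offer, and a statistical analysis plan could say how kits enter uptake. But section 3.5 fixes the source as Exeter and section 3.3.3 says the results are not there. Anyone following the protocol would score these women as non-attenders.
- **One routine outcome in all arms is a defensible choice** for a trial embedded in the screening programme. This stands as a reason to keep Exeter attendance as a reported outcome. It does not make that outcome a measure of self-sampling's effect, nor does it justify the common 10-point planning difference.
- **The size rests on borrowed inputs.** This stands in part. The 10% positivity is from one cited cohort, and the table shows how the result moves. The 10% control rate is described as attendance by the next recall. If it were 5% at 12 months (an assumption), a 2.25-point gain would have power of 10-14% at ICC 0.07 and 16-22% at ICC 0.026, which is still low.
- **A reader might infer that the pilot could wrongly have dropped self-sampling**, since its rule rests on "comparing the uptake rate in the pilot interventions and the control is rejected at a one-tailed 25% significance level". The documents do not support this. Section 3.4 does not tie pilot uptake to Exeter, section 8.1 speaks of the response to unsolicited kits, and both self-test arms are already in phase 2.
- **A reader might call every returned kit a true gain in screening.** The protocol does not support that either: self-sampling is there to decide who needs cytology, so an HPV-positive woman without cytology has not completed the pathway.
- **The data link is not trivial.** This stands. Agency data are anonymised, and consent to check Exeter is tied to a positive result.

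**Conclusion.** The point holds. As written, the primary outcome leaves out most completed self-tests. The bias runs against self-sampling, fully in two arms and partly in two more. On the protocol's own cited figures, 2.25 points can register against the 10 powered for, with power of about 6-7% at ICC 0.07 and about 11% at ICC 0.026. Of the assumed positivity rates at 25% uptake and ICC 0.07, only 40% brings power back above 80%.

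These figures rest on 25% uptake, 90% of positives going on to cytology, a 10% control rate, two-sided alpha 0.01 and equal clusters. The near-nil gain rests further on negative self-testers forgoing cytology that they would otherwise have had. A recorded deficit is not established: the lower end is 0.25 points below control, and only under that assumption.

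**What to change.** 1. In sections 3.5 and 5.2, define the phase 2 primary outcome in all arms as cytology recorded on Exeter, or a self-sample returned with a valid HPV result, by 12 months post-call.
2. Ask the screening agency, which is already notified of results, to add a dated self-test flag to each anonymised record. No woman is then counted twice and no identifiable data need pass to the trial team.
3. Check that the kit consent wording covers this use for HPV-negative women. It already covers reporting results to the agency, but permission to check Exeter is tied to a positive result.
4. Report Exeter cytology attendance in all arms, and cytology completion among HPV-positive women, as secondary outcomes.
5. Restate the phase 2 power in section 5.1.2 for the chosen definition.
6. State in section 3.4 that pilot uptake uses the same definition.

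The cost is a revised endpoint definition, an added field that the agency must confirm it can supply, a consent check and a new power statement. The downside is that the outcome combines two kinds of test and counts HPV-positive women who have not yet had cytology. The secondary outcomes in item 4 show both parts.
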